13.2 Analysis Plan

The analysis for this trial will commence at planned time points and at the time the patients have become evaluable for the primary endpoint. Such a decision will be made by the Statistician and Study Chair, in accord with ETCTN Standard Operating Procedures, availability of data for secondary endpoints (e.g. laboratory correlates), and the level of data maturity.

13.2.1 Phase 1 Safety Run-in Primary Analysis

All patients that have received any amount of the combination anetumab ravtansine and pembrolizumab will be evaluable for toxicity. Please note this is different from the definition of evaluable for dose-limiting toxicity (DLT) where patients who cannot complete the planned dose due to reasons other than toxicity will be replaced.

13.2.2 Randomized Phase 2 Primary Endpoint Estimation

The proportion of successes will be estimated in each group by the number of successes

divided by the total number of evaluable patients. Confidence intervals for the true success proportion will be calculated in each arm. Comparison of confirmed response rates between the two treatment groups will be performed using a one-sided z-test with pooled variance at significance level 0.10.

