13.1.3.3 Randomized Phase 2 Study

Decision Rule: A randomized phase 2 trial comparing combination therapy with anetumab ravidansine and pembrolizumab as compared to pembrolizumab alone will be conducted, once a safe combination of doses is identified. We will enter 49 evaluable patients on each arm (98 total) of the study using a 1:1 randomization scheme utilizing the permuted block procedure, where patients are stratified based on ECOG performance score (0 vs. 1). A sample size of 49 patients per arm provides 80% power to detect an improvement in response rate from 20% to 40%, using a one-sided test at a significance level of 0.10. The baseline response rate of 20% is based on a prior study⁷³. In addition, this trial implements a group sequential design with a single interim analysis, adopting the Rho family (Rho=2) beta spending function for controlling the overall type II error rates. The interim and final analysis boundaries and characteristics were generated using the East 6 clinical trial software program (version 6.4, Cytel Inc.).

The Z-score will be calculated for testing the null hypothesis that the difference of response rates between two arms is equal to zero, based on the normal approximation with pooled variance of standardized test statistics. The study design will be implemented as follows:

Interim Analysis Decision Rule: An interim analysis will be performed for futility. After the first 25 patients randomized into each arm (the first 50 patients in both arm) become evaluable for the primary endpoint, if the z-score is less than -0.072, we will terminate accrual and consider this early evidence that the experimental arm does not have a higher overall response rate and accrual will be terminated. Otherwise, we will continue accrual.

Final Decision Rule: If the interim analysis criteria are met for full accrual, a total of 49 evaluable patients per arm will be enrolled into this study. At the final analysis, it will be concluded that the experimental arm (combination therapy) is superior to the control arm (pembrolizumab alone), if the z-score is greater than 1.282. This will be considered sufficient evidence that the experimental arm may be recommended for further testing in subsequent studies. Otherwise, we will conclude that there is no statistical evidence of superiority of the experimental regimen (combination therapy).

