13.4 Stratification Factors

13.4.1 For the randomized phase 2: ECOG performance score: 0 vs. 1

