13.5.2 Overall Survival

Overall survival is defined as the time from the start of treatment to death due to any cause. The distribution of survival time will be estimated using the method of Kaplan-Meier. The comparison of overall survival between two treatment arms will be based on the log-rank test.

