13.5.3 Progression Free Survival

Progression free survival is defined as the start of treatment to the earliest date that

disease progression is objectively documented or death due to any cause. The distribution of progression-free survival will be estimated using the method of Kaplan-Meier. The comparison of progression-free survival between two treatment arms will be based on the log-rank test.

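### Randomization is stratified by ECOG, but the primary z-test and the PFS and OS log-rank tests ignore it, so they are somewhat conservative if ECOG is prognostic

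*Combined protocol and SAP*

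**What the plan says.** Section 13.4 lists one stratification factor: "For the randomized phase 2: ECOG performance score: 0 vs. 1". Section 13.1.3.3 describes permuted blocks, 1:1, within those two groups.

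The tests do not refer to it. Section 13.1.3.3 defines the z-score for the interim and final looks as "based on the normal approximation with pooled variance of standardized test statistics", with futility below -0.072 and success above 1.282. Section 13.2.2 repeats it for the final comparison: "Comparison of confirmed response rates between the two treatment groups will be performed using a one-sided z-test with pooled variance at significance level 0.10". For the time-to-event endpoints, 13.5.3 says "The comparison of progression-free survival between two treatment arms will be based on the log-rank test" and 13.5.2 says "The comparison of overall survival between two treatment arms will be based on the log-rank test". Section 13 plans no ECOG-stratified or ECOG-adjusted analysis, even as a sensitivity analysis.

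**The concern.** Stratified blocks keep the arms balanced on ECOG, so differences between ECOG 0 and ECOG 1 patients add almost nothing to the variability of the arm comparison. An unstratified variance still counts those differences. If ECOG is prognostic, the standard error is too large, and the test rejects less often than its nominal level. For the log-rank test, pooling unlike strata also pulls the hazard ratio towards 1.

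What is at stake is power, not validity. PFS is the first secondary objective (Section 1.2.1), and the trial yields only about 75-78 PFS events under the assumptions below.

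**Working it through.** **The plan's own figure.** Inputs from 13.1.3.3: 49 per arm, 20% vs 40%, one-sided 0.10. With pooled rate 0.30, the null standard error is sqrt(2 × 0.30 × 0.70 / 49) = 0.0926. The alternative standard error is sqrt((0.20 × 0.80 + 0.40 × 0.60) / 49) = 0.0904. Power = Φ((0.20 - 1.282 × 0.0926) / 0.0904) = Φ(0.90) = 0.816. Simulating the full rule with its futility look gives 0.817 with exactly 25 per arm at the interim, and 0.811 with blocks within ECOG. The plan states 80% in the text and 0.805 in its table, so its power reproduces for the unstratified test. (The table's 0.009 chance of declaring success at zero difference does not reproduce; simulation gives about 0.095. That is a separate matter.)

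**Direction, analytically.** Under the null, let p be the overall response rate, w the ECOG 0 share, and p0, p1 the stratum rates. The pooled test uses p(1 - p). The variance left after stratified randomization is p(1 - p) - w(1 - w)(p0 - p1)². Take p = 0.20 and w = 0.5:

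- ECOG odds ratio 3 (28.3% vs 11.7%): 0.16 - 0.25 × 0.166² = 0.153, ratio 0.957. The level is 1 - Φ(1.282 / sqrt(0.957)) = 0.095.
- Odds ratio 5 (31.6% vs 8.4%): 0.16 - 0.25 × 0.232² = 0.147, ratio 0.916, level 0.090.

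**Primary test, full design, simulated.** 200,000 trials per scenario; 98 patients; interim after 50; thresholds -0.072 and 1.282. Blocks of 4, the ECOG mix and the ECOG odds ratio are assumptions. For a 50/50 mix and a constant 20-point difference:

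| ECOG odds ratio | Size, planned | Size, CMH | Power, planned | Power, CMH |
|---|---|---|---|---|
| 1 | 0.097 | 0.098 | 0.811 | 0.809 |
| 2 | 0.094 | 0.097 | 0.812 | 0.813 |
| 3 | 0.091 | 0.096 | 0.815 | 0.820 |
| 5 | 0.088 | 0.097 | 0.820 | 0.830 |

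Across ECOG 0 shares of 30%, 50% and 70%, and with the effect also run as a common odds ratio, stratifying changes power by about -0.2 points (odds ratio 1), 0 to +0.3 (2), +0.2 to +0.8 (3) and +0.4 to +1.8 (5). The planned test never falls below 0.809. Futility stopping under the null is 0.456-0.460 planned and 0.457-0.464 with CMH; the plan gives 0.458. Under the alternative it is 0.039-0.048 and 0.040-0.048.

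**PFS, simulated.** 80,000 trials per scenario, exponential times. The control median of 6.2 months comes from another pembrolizumab trial cited in Section 2.2.2. Accrual of 34 months and analysis at 39.5 months come from 13.3.2. Assumed: treatment hazard ratio 0.6, no dropout, and one-sided 0.10, because the plan sets no level for PFS or OS. The first two result columns are for a 50/50 mix. The last covers the mixes run, with changes taken before rounding.

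| ECOG hazard ratio | Null size, unstratified / stratified | Power, unstratified / stratified | Power change, points |
|---|---|---|---|
| 1 | 0.104 / 0.104 | 0.831 / 0.823 | -0.6 to -0.7 |
| 1.5 | 0.098 / 0.102 | 0.819 / 0.822 | +0.3 to +0.4 |
| 2 | 0.091 / 0.102 | 0.795 / 0.819 | +2.0 to +2.4 |
| 3 | 0.079 / 0.103 | 0.741 / 0.812 | +6.1 to +7.1 |

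At one-sided 0.025 the changes are -0.9 to -1.0, +0.7 to +1.1, +4.1 to +4.6 and +10.6 to +12.2 points. Separate code at two-sided 0.05 agrees: power 0.578 / 0.586, 0.531 / 0.571 and 0.450 / 0.577 at ECOG hazard ratios 1.5, 2 and 3. OS was not simulated.

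**The case against.** The strongest reply is that nothing is broken. The same unstratified test appears consistently in 13.1.3.3 and 13.2.2, the sample size and boundaries were built for it, and it meets its power in every scenario. For response the gain is under 1 point unless ECOG is very strongly prognostic. Part of the shortfall from 0.10 is present even at odds ratio 1 (size 0.097). All of this stands, and it limits the point to efficiency and consistency.

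The larger PFS figures need an ECOG hazard ratio of 3 within a population already restricted to ECOG 0 or 1 (Section 3.2.2.3). No document supports that value, and at 1.5 the gain is slight. This also stands, which is why the result is given as a range.

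The change may come too late to replace the main analysis. This is Amendment 16, the phase 2 dose is already chosen (2.3.2.2), response is judged by the local investigator (11.1.8), and the principal investigator and statistician can see the data at any time (12.1). The documents do not say whether phase 2 outcomes exist. The fix therefore depends on that.

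Two smaller points are fair. The operating-characteristics table in 13.1.3.3 would need to be rerun for the new statistic. The simulation also analyses 98 patients exactly as randomized, whereas the plan accrues up to 110 and drops ineligible or untreated patients (13.1.2, 13.3.1), so balance within ECOG would be only approximate. Neither removes the case for using the factor.

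**Conclusion.** The concern holds. The trial randomizes within ECOG and analyses as though it had not. If ECOG is prognostic, the planned tests err in the conservative direction. Validity and the stated 80% power for response are intact.

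For response, the power forgone is at most 0.8 points up to an ECOG odds ratio of 3, and 1.8 at 5. For PFS at one-sided 0.10 it is about 2 points at an ECOG hazard ratio of 2 and 6-7 at 3, and larger at a stricter level. If ECOG is not prognostic there is no loss, and stratifying would itself cost a little. These sizes rest on assumed ECOG effects, ECOG mix, block size, PFS treatment effect and PFS significance level, none of which the documents give. The case for change rests mainly on PFS and on matching the analysis to the randomization.

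**What to change.** - **13.5.2 and 13.5.3:** use log-rank tests stratified by ECOG (0 vs 1) as recorded at randomization.
- **13.1.3.3 and 13.2.2:** use the ECOG-stratified CMH z statistic at both looks with -0.072 and 1.282 unchanged. Report a stratum-weighted risk difference with its confidence interval, and keep the unstratified z-test as a sensitivity analysis.
- **If outcome data by arm have already been seen:** keep the planned tests as the main analysis and add the stratified ones as sensitivity analyses.
- **13.5.1:** leave duration of response unstratified. With 0.20 × 49 = 9.8 to 0.40 × 49 = 19.6, there are only about 10-20 responders per arm.

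The cost is analysis wording and a rerun of the operating-characteristics table. Sample size, thresholds and data collection do not change. If ECOG proves not to be prognostic, the price is about 0.2 points of power for response and 0.6-0.7 for PFS at one-sided 0.10. With a 30/70 mix the smaller stratum has about 15 patients at the interim (0.30 × 50) and 29 at the end (0.30 × 98). The stratified final test, taken alone, still holds its level there (0.101-0.102).

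### The primary response test ignores ECOG, the only randomization stratum; a prespecified ECOG-stratified test would be a small, cheap improvement to a valid plan

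*Combined protocol and SAP*

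**What the plan says.** Section 13.1.3.3 randomizes 1:1 in permuted blocks stratified by ECOG. Section 13.4 lists one factor only: "ECOG performance score: 0 vs. 1". The z-score for the difference in response rates is "based on the normal approximation with pooled variance of standardized test statistics". It serves both decisions: stop for futility if it is below -0.072 after 25 patients per arm, and declare superiority if it exceeds 1.282 at 49 per arm. Section 13.2.2 repeats that the comparison "between the two treatment groups will be performed using a one-sided z-test with pooled variance at significance level 0.10".

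On design properties, section 13.1.3.3 states: "A sample size of 49 patients per arm provides 80% power" for 20% against 40%, "using a one-sided test at a significance level of 0.10".

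No section gives an ECOG-stratified or ECOG-adjusted primary test, a sensitivity analysis by ECOG, or a reason for leaving the factor out. Section 13.1.2 restricts the analysed set to eligible patients who started treatment, and section 13.3.1 plans 12 extra patients to cover ineligibility, cancellation and similar losses.

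**The concern.** Stratified blocks balance the arms on ECOG. If ECOG predicts response, that balance removes between-stratum variation from the treatment difference, but the pooled variance p(1-p) still counts it. The standard error is then a little too large, the null standard deviation of z is below 1, and a cut of 1.282 is stricter than one-sided 0.10.

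There is a second, separate consideration. Ineligible and untreated patients are dropped after randomization, so balance in the analysed set is not guaranteed. An unstratified test does not correct for whatever imbalance results.

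At stake is a small amount of efficiency, and some robustness, in the test that decides whether the combination goes forward.

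**Working it through.** **Step 1. Reproduce the plan's power.** Inputs from section 13.1.3.3: 20% vs 40%, 49 per arm, one-sided 0.10. Ignoring the interim look:

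power = Φ([d√n - z√(2·p̄·q̄)] / √(p₁q₁ + p₂q₂)) = Φ([0.20 × 7 - 1.2816 × √0.42] / √0.40) = Φ(0.569/0.632) = Φ(0.900) = 0.816.

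With both looks (25 then 49 per arm, boundaries -0.072 and 1.282), a bivariate normal calculation gives 0.805 and binomial simulation gives 0.816. The plan states 80%, and 0.805 in its operating-characteristics table. The power reproduces. (The same table prints 0.009 for success at zero difference, where the design recomputes to about 0.096. That looks like a misprint and has nothing to do with stratification.)

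**Step 2. Mechanism.** With exact ECOG balance, ECOG 0 share f, response gap g between strata and overall rate p, the null variance of the unstratified z is approximately

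1 - f(1-f)g² / [p(1-p)].

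For f = 0.49, g = 0.20, p = 0.20: 0.2499 × 0.04 / 0.16 = 0.0625. The SD is √0.9375 = 0.968, and the single-look size is 1 - Φ(1.282/0.968) = 0.093. For g = 0.30 the subtracted term is 0.1406, the SD 0.927 and the size 0.083.

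**Step 3. Simulate the written two-look rule.** These inputs are assumptions, because the documents give none of them: one third or one half ECOG 0, exact balance, mean response 20% vs 40%, and an ECOG odds ratio (OR) for response of 1 to 4. CMH uses no continuity correction and the same boundaries.

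| ECOG OR | Pooled size | CMH size | Pooled power | Power change with CMH (points) |
|---|---|---|---|---|
| 1 | about 0.095 | about 0.097 | 0.816-0.817 | about -0.35 |
| 2 | 0.093 | about 0.097 | 0.819 | about 0 |
| 3 | about 0.090 | 0.097-0.099 | 0.824 | +0.4 to +0.7 |
| 4 | 0.087-0.088 | 0.097-0.100 | 0.828-0.830 | +0.7 to +1 |

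Of the distance to 0.10 at OR 3, 0.100 - 0.095 = 0.005 is present with no ECOG effect, and only 0.095 - 0.090 = 0.005 comes from pooling. At OR 4 the ECOG part is 0.007 to 0.008.

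A more extreme assumption is a 30-point response gap, for example 35.3% vs 5.3% (OR 0.546/0.056 = 9.7) or 40.8% vs 10.8% (OR 0.689/0.121 = 5.7). Pooled size is then 0.079-0.082 and CMH size 0.099-0.101, with about 1 point more power for CMH.

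**Step 4. Futility look.** Under exact balance the stopping probability is identical for the two statistics: 0.42-0.43 under the null and 0.03-0.04 under the alternative. The boundary is so close to zero that a slightly different variance does not move any outcome across it.

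**Step 5. Imbalance in the analysed set.** Conditional on a fixed ECOG imbalance at OR 3, with about half the patients ECOG 0:

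| ECOG 0 patients, experimental vs control (of 49 each) | Pooled | CMH |
|---|---|---|
| 26 vs 22 | size 0.122 | size 0.097 |
| 27 vs 21 | size 0.138 | size 0.095 |
| 4 fewer in the experimental arm | power 0.769 | power 0.820 |
| 6 fewer in the experimental arm | power 0.738 | power 0.817 |

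These results are conditional on the stated imbalance. Averaged over ECOG splits left entirely to chance, the pooled test keeps a size of 0.095 for OR 1 to 4.

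**The case against.** The strongest reply is that nothing here is an error. The rule is fully specified, is the same in both sections, inflates no error rate, and keeps power above 80% in every balanced scenario. An unstratified comparison after stratified randomization is a common choice in a 98-patient screening trial. CMH gains nothing until the ECOG odds ratio passes about 2 and loses a little if ECOG is not prognostic, and the documents do not show which case applies. All of that stands.

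The two arguments for stratifying also pull in different directions. Conservatism needs ECOG balance, and exclusions that disturb balance reduce it. They are alternative reasons for the same change and should not be added together.

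Changing the primary statistic has a procedural cost too. The boundaries and table were produced for this z-score, and section 12.1 gives the principal investigator and statistician access to the data at all times. A late change would need assurance that it was not prompted by results. This stands as well and governs the timing of the fix.

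A reader might infer that pooling distorts the futility decision because the same z-score is used there. Step 4 shows no difference under balance, so no defect is demonstrated at that look. A reader might also attribute the whole gap below 0.10 to pooling, but about 0.005 of it exists with no ECOG effect.

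**Conclusion.** The mismatch between the stratified randomization and the unstratified primary test is real. Its effect is small and conditional. With the arms balanced on ECOG, the two-look size drops from about 0.095 to about 0.090 at an assumed ECOG odds ratio of 3 and to 0.087-0.088 at 4. The power at issue is at most about 1 point over that range. The plan remains valid and meets its stated 80% power.

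The documents do not support reading this as an invalid or underpowered go/no-go rule, nor as a test that has lost its type I error control through post-randomization exclusions. The imbalance results assume a particular split, and the documents contain nothing to show that such a split will occur.

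What remains is a low-cost improvement: use the one factor the design already balances, and gain protection if the analysed set turns out unbalanced. The size of the benefit rests on assumed ECOG shares and prognostic strength.

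**What to change.** In sections 13.1.3.3 and 13.2.2, define the z-score at both looks as the Cochran-Mantel-Haenszel statistic stratified by ECOG (0 vs 1), without continuity correction. Keep the boundaries -0.072 and 1.282. Beside the per-arm rates, report the Mantel-Haenszel risk difference with its interval; section 13.2.2 currently plans intervals for each arm only. Rerun the operating-characteristics table in section 13.1.3.3 for the new statistic, stating the assumed ECOG mix and prognostic strength.

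The change should be fixed and dated before any comparative response data are reviewed. If that is no longer possible, keep the decision rule as written and add the stratified test as a prespecified sensitivity analysis.

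The cost is a sentence in each of two sections, the re-simulation, and about 0.3 points of power if ECOG turns out not to be prognostic. No new data are needed, because ECOG is already recorded for randomization.

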13.3 Sample Size/Accrual Rate

13.3.1 Sample Size

The phase 1 safety lead-in is expected to require a minimum of 12 patients and a maximum of 24 patients. The randomized phase 2 portion of this study is expected to require a minimum of 50 and a maximum of 98 evaluable patients. We anticipate accruing an additional 12 patients during the phase II portion of the trial to account for ineligibility, cancellation, major treatment violation, or other reasons. Therefore, the phase II portion is expected to accrue a maximum of 110 patients and overall sample size will be a maximum of 134 patients.

13.3.2 Accrual Rate and Study Duration

The anticipated accrual rate is approximately 4-5 patients per month. Therefore, the accrual period for phase 2 portion is expected to be about 34 months. The final analysis can begin approximately 39.5 months after the phase 2 portion begins, i.e. as soon as the final patient randomized to this trial has been followed for at least 18 weeks.

13.3.3 Inclusion of Women and Minorities

This study will be available to all eligible patients, regardless of race, gender or ethnic origin.

There is no information currently available regarding differential effects of this regimen in subsets defined by race or gender, and there is no reason to expect such differences to exist. Therefore, although the planned analysis will, as always, look for differences in treatment effect based on racial and gender groupings, the sample size is not increased in order to provide additional power for subset analyses.

Based on prior studies involving similar disease sites, we expect about 20-25% of patients will be classified as minorities by race and about 40% of patients will be women. The expected sizes of racial by gender subsets are shown in the following table:

PLANNED ENROLLMENT REPORT

Racial Categories	Ethnic Categories				Total
	Not Hispanic or Latino		Hispanic or Latino		
	Female	Male	Female	Male	
American Indian/ Alaska Native	1	2	0	0	3

Racial Categories	Ethnic Categories				Total
	Not Hispanic or Latino		Hispanic or Latino		
	Female	Male	Female	Male	
Asian	1	1	0	0	2
Native Hawaiian or Other Pacific Islander	0	1	0	0	1
Black or African American	1	3	0	0	4
White	36	51	7	10	104
More Than One Race	3	6	4	7	20
Total	42	64	11	17	134

13.4 Stratification Factors

13.4.1 For the randomized phase 2: ECOG performance score: 0 vs. 1

13.5 Analysis of Secondary Endpoints

13.5.1 Duration of Response

Duration of response is defined for all evaluable patients who have achieved a response as the date at which the patient's objective status is first noted to be a PR or CR to the earliest date progression is objectively documented. If a patient has not had disease progression, they will be censored on the date of their last disease assessment. The distribution of duration of response will be estimated using the method of Kaplan-Meier. The comparison of duration of response between two treatment arms will be based on the log-rank test. This calculation will start with the date of start of treatment.

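### Duration of response is tested between arms in responders only, so its log-rank p-value is not a randomized comparison and can mislead in either direction

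*Combined protocol and SAP*

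**What the plan says.** Section 13.5.1 limits the endpoint to responders: "Duration of response is defined for all evaluable patients who have achieved a response". It plans Kaplan-Meier estimates and then a test: "The comparison of duration of response between two treatment arms will be based on the log-rank test". The sidedness, significance level and stratification of this test are not given. The test is not labelled descriptive, and no version covering all patients is planned.

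On censoring, the section says "If a patient has not had disease progression, they will be censored on the date of their last disease assessment". It closes with "This calculation will start with the date of start of treatment", which conflicts with the origin given at the start of the same paragraph (first PR or CR).

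The design in Section 13.1.3.3 is built on a difference in response: "A sample size of 49 patients per arm provides 80% power to detect an improvement in response rate from 20% to 40" per cent, "using a one-sided test at a significance level of 0.10". Sections 13.5.2 and 13.5.3 compare overall survival and progression-free survival by log-rank without restricting them to responders.

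**The concern.** Response is observed after randomization, and the combination is meant to change it. If the combination works as planned, its responders are a mixture of patients who would have responded to pembrolizumab anyway and patients who respond only because anetumab ravtansine was added. The control responders contain only the first kind. A difference in duration between the two groups can then come wholly from their make-up, with nobody's response shortened or lengthened. The problem is largest when the trial succeeds on its primary endpoint.

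What is at stake is how this secondary endpoint is read. There is also one point of conduct: the Other Considerations paragraph of Section 13.1.3.3 lists the quality and duration of response among the matters to be weighed in any decision to end the study.

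**Working it through.** **Plan's own figure.** The documents give no power for duration of response, so the check starts from the primary design. For 49 per arm, 20% vs 40%, one-sided 0.10 and pooled variance, power = Φ[(0.20 × √49 − 1.2816 × √(2 × 0.30 × 0.70)) / √(0.20 × 0.80 + 0.40 × 0.60)] = Φ[(1.400 − 0.831) / 0.632] = Φ(0.900) = 0.816. Simulating the stated boundaries (−0.072 at 25 per arm, 1.282 at 49 per arm) also gives 0.816. The plan states 80%, and 0.805 in its table of operating characteristics, so the design reproduces to within about one point.

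**Numbers entering the log-rank test.** Control: 49 × 0.20 = 9.8 responders. Combination: 49 × 0.40 = 19.6, of whom 9.8 are added responders if the other 20% would respond on either arm.

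**Simulation.** 20,000 trials per scenario, 49 per arm, exponential durations, 24 months of follow-up. Patients who respond on either arm have a median of 12 months in both arms. A further 20% respond only on the combination, with median m. All durations are assumptions, because the documents give no medians for this setting.

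Two rows of the table follow by formula:
- The median duration in all combination responders solves 0.5 × 2^(−t/12) + 0.5 × 2^(−t/m) = 0.5.
- Mean time in response over 24 months in all patients, with non-responders at zero, uses τ(m) = (m / ln 2) × (1 − 2^(−24/m)). Control is 0.2 × τ(12) = 0.2 × 12.98 = 2.6 months. The combination is 0.2 × τ(12) + 0.2 × τ(m); for m = 4, 2.60 + 0.2 × 5.68 = 3.7.

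| Median in added responders, m (months) | 4 | 6 | 12 | 20 | 30 |
|---|---|---|---|---|---|
| Significant against combination (two-sided 0.05) | 16% | 10% | 2% | 0.5% | 0.2–0.3% |
| Significant for combination (two-sided 0.05) | 0.3% | 0.7% | 4% | 10% | 16% |
| Log-rank statistic points against combination | 84% | 76% | 50% | 30% | 19% |
| Median duration, all combination responders (control 12) | 6.6 | 8.3 | 12 | 15.3 | 18.4 |
| Mean time in response, all patients (control 2.6) | 3.7 | 4.2 | 5.2 | 5.9 | 6.3 |

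With equal durations (m = 12) there is no directional bias. Away from that point the test follows the make-up of the responder group, while the all-patient mean favours the combination throughout.

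**Sensitivity to follow-up.** Section 13.3.2 gives 34 months of accrual and a final analysis at about 39.5 months. If response is seen at the first 9-week scan (2.1 months), follow-up from response runs from 39.5 − 34 − 2.1 = 3.4 months to 39.5 − 2.1 = 37.4 months. With censoring uniform over that range, the rates against are about 15% (m = 4) and 9% (m = 6), and the rates in favour about 9% (m = 20) and 15% (m = 30).

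**Sensitivity to significance level.** If the test were read at one-sided 0.10, as the primary endpoint is, the rates against would be 39%, 27% and 9% for m = 4, 6 and 12 (censoring uniform over 12 to 36 months).

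**The case against.** The strongest reply is that little depends on this test. Superiority rests only on the response-rate z-score, duration of response is not among the secondary objectives in Section 1.2, and PFS and OS already supply time-to-event comparisons not limited to responders. Even at m = 6, about 90% of trials show no significant result against the combination. All of this stands, and it limits the weight of the point. It does not make the p-value meaningful.

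A reader might infer that the test is tilted against the combination. The documents do not support that. Their only duration figures for anetumab ravtansine point the other way: Section 2.2.1 reports that four of five responders at the maximum tolerated dose stayed in response beyond 600 days (600 / 30.4 = about 20 months). Five monotherapy responders are weak evidence, but nothing in the documents supports 4 to 6 months instead. A falsely favourable result is at least as plausible as a falsely adverse one.

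A reader might also infer that a hazard ratio will be reported; Section 13.5.1 plans none. Nor does Section 13.8.2 already settle the matter. It asks that conclusions rest on all eligible patients, but its limit on sub-analyses concerns exclusions for protocol deviations and does not mention duration of response.

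Finally, an all-patient measure answers a different question from how long responses last. With equal durations and a 12-month window it favours the combination in 97% of trials simply because there are more responders. That also stands.

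**Conclusion.** The point holds as a flaw of structure: the planned test conditions on the primary endpoint, so it is not a randomized comparison and its p-value does not test an effect on duration. At the planned response rates, and with a 12-month median in patients who respond on either arm, false significance reaches about 16% against the combination (m = 4) or about 16% for it (m = 30). It shows no directional bias when added responders have the same durations as the others. These sizes rest on assumed exponential durations and on the 20% / 40% design rates; the argument itself does not. The effect is confined to interpretation of this secondary endpoint and to the termination consideration in Section 13.1.3.3. The primary conclusion is not at risk.

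**What to change.** Delete the log-rank sentence from Section 13.5.1 and report Kaplan-Meier duration of response by arm descriptively, without a p-value. In the same edit, settle the time origin and state how death without documented progression is handled, since the descriptive curves depend on both.

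If a between-arm statement is wanted, there are two options. One is to rely on the planned PFS comparison. The other is mean time in response in all patients of the primary analysis set, with non-responders counted as zero. A fixed 12- or 24-month window would be partly censored: the final analysis may begin once the last patient has 18 weeks of follow-up (Section 13.3.2), and follow-up after treatment is for vital status only (Section 5.6). The estimate therefore needs a method that handles censoring, over a window that the follow-up supports.

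The cost is a change of wording and, if the all-patient measure is chosen, one more programmed estimate. No new data are needed, and the primary endpoint and sample size are unchanged. The downside is that duration of response loses its formal p-value and the all-patient measure partly repeats the response-rate difference.
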